5.3 Selection of Trial Population

Only patients meeting all inclusion criteria and no exclusion criteria may be enrolled into the trial as subjects. Prior to performing any trial assessments which is not part of the subject's routine medical care, the investigator will ensure that the subject or the subject's legal representative has provided written informed consent following the procedure described in Section 9.2.

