5.4 Criteria for Initiation of Trial Treatment

When subjects enter this study, they will be randomized to either of the two treatment groups at ratio 1:1 by the randomization schedule generated by a computer program. Considering these two treatments have differences in both administration route and dose, this study is open-label, randomized, controlled clinical study.

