7.2.1 Screening/Baseline

At the initial study visit, the subject will be informed of the study objectives and overall requirements, and written informed consent will be obtained prior to any study specific assessments. The subject will then undergo a brief clinical evaluation to ensure compliance with the inclusion and exclusion criteria to determine the eligibility (see Section 5.2).

Data for all subjects will come from the subjects' Screening or Baseline Visits and the subjects' medical records:

The following must be completed before Gn Initiation:

- Visit date
- Subject Name and hospital subject number will be recorded and kept confidentially in the clinic solely for the purposes of generating a unique study subject number which will be used to anonymously identify each subject in the study.
- Demographic details including age, gender, date of birth and ethnic origin
- Weight and height
- Clinical and gynecological examination
- Gynecological history: duration of infertility, menstrual cycle, History of miscarriages, history of pelvic surgery; history of ovarian surgery.
- Medical history and concomitant illness
- Any concomitant medication taken by the subject when entering the study
- Concomitant medications prescribed and reasons
- Ability to conceive and times of IVF attempts
- In vitro fertilization-embryo transfer and ICSI indications assessment
- The following data should be collected (data within 3 months before Screening is accepted)
 - FSH and estrogen (E2) levels during the early follicular phase (Cycle Day 2 to 4)
 - AFC (follicles ≥ 2 mm and < 11 mm) assessed in the early follicular phase (Cycle Day 2 to 4)

After randomization, blood samples for AMH test should be collected in each site, and the analysis will be performed in central lab. The analysis result of AMH test will be used in final statistical analysis, not for guiding the clinical medication.

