8.5.2 Analysis of Primary Endpoints

The result of the analysis of the primary endpoint (CLBR) is essential for the non-inferiority claim. The conservative CLBR will be used to test the hypothesis in a confirmatory way.

Definition of the primary endpoint: CLBR with first live birth resulting from one initiated COS cycle.

Numerator is the No. of women got their first live birth, the Denominator is the No. of women who attempt the ovarian stimulation.

There will be two ways to calculate the CLBR:

- The conservative estimate of the cumulative live birth rate, which is based on the assumption that none of the women who do not return for a subsequent embryo transfer would have had a live birth.
- The optimal estimate of the cumulative live birth rate, which is based on the assumption that women who do not return for a subsequent embryo transfer would have had the same live birth rates as those who do return.

Conservative CLBR with the corresponding 95% confidence interval (CI) will be based on binominal distribution. The two treatments will be compared by using Chi-square test for conservative CLBR. The difference between the two treatments and its associated 95% CI based on asymptotic normal distribution will be presented. If the lower-limit of the 95% confidence interval is greater than the non-inferiority limit (-10%), the null hypothesis will be rejected and it would be claimed that GnRH antagonist protocol is non-inferior to GnRH agonist protocol regarding to the cumulative live birth rate.

Optimal CLBR will be analyzed by using Kaplan-Meier product-limit method, the rate and its 95% CI will be provided. For optimal CLBR, the two treatments will be compared using Kaplan-Meier

product-limit estimates, the difference between the two treatments and its associated 95% CI will be also presented.

Number of oocytes retrieved will be summarized and compared basing on analysis of variance (ANOVA) including treatment and center as factors. The treatment difference and the two-sided 95% confidence interval will be reported.

Furthermore, univariate/multivariate logistic or cox regression analysis will be performed to evaluate the dependence of Age (≤ 35 or > 35 years), AFC, AMH, number of oocytes retrieved, number of usable embryos, times of embryo transfer, and BMI in relation to pregnancy rate or CLBR.

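### The ANOVA for number of oocytes retrieved is valid, but adding baseline AFC and age would probably sharpen its treatment difference at almost no cost (free improvement, low priority)

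*Combined protocol and SAP*

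**What the plan says.** Section 8.5.2 and the statistical methods in the synopsis give the same model for the oocyte count: "Number of oocytes retrieved will be summarized and compared basing on analysis of variance (ANOVA) including treatment and center as factors". The output is also fixed: "The treatment difference and the two-sided 95% confidence interval will be reported". Neither place names a covariate.

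The two candidate covariates are collected at Screening/Baseline (section 7.2.1): "AFC (follicles ≥ 2 mm and < 11 mm) assessed in the early follicular phase (Cycle Day 2 to 4", and "Demographic details including age, gender, date of birth and ethnic origin". Section 5.3.1 makes both entry criteria, with AFC from 8 to 20 and age of at most 38.

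Section 5.3 states that "Only patients meeting all inclusion criteria and no exclusion criteria may be enrolled into the trial as subjects", and section 5.4 that "When subjects enter this study, they will be randomized to either of the two treatment groups at ratio 1:1". AMH is different: "After randomization, blood samples for AMH test should be collected in each site" (section 7.2.1).

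Age and AFC do appear as regressors in section 8.5.2, but only in logistic or Cox models. The list there runs on to "number of usable embryos, times of embryo transfer, and BMI in relation to pregnancy rate or CLBR". Oocyte number is a regressor in those models, not an outcome.

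**The concern.** For a continuous outcome, a linear model that includes baseline variables related to the outcome has a smaller residual variance. It therefore gives a narrower confidence interval for the same treatment difference. AFC and age, with FSH and E2, are what the eligibility criteria use to select women with normal ovarian reserve, so it is reasonable to expect them to be related to oocyte yield. Section 6.3 refers to section 8.2 for stratification, but section 8.2 names no stratification factor, so the design does not balance either variable.

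What is at stake is the precision of one secondary comparison. It has some interpretive value: the background in section 3 cites a review that found fewer oocytes with the antagonist protocol, and the oocyte difference will be read alongside the CLBR result.

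**Working it through.** **Timing of the covariates.** Section 7.2.1 says only that baseline items must be complete before gonadotrophin initiation. That AFC and age are known before randomisation follows from sections 5.3, 5.3.1 and 5.4 together: both are entry criteria, only women who meet all criteria may be enrolled, and randomisation takes place at study entry. AMH fails this test.

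**Whether another section already covers the point.** No section adds a covariate-adjusted analysis of oocyte number. Section 8.5.1 defers only missing-data methods to a statistical analysis plan.

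**The plan's own sample size (section 8.1).** Inputs: CLBR 60% in both arms, margin 10 percentage points, two-sided 95% interval, 80% power.

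- n per arm = (1.960 + 0.842)² × (0.24 + 0.24) / 0.10² = 376.8, rounded up to 377
- 377 / (1 − 0.15) = 443.5, rounded up to 444 per arm, or 888 in total

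Both figures match the plan. It gives no precision or power figure for oocytes, so there is nothing to reproduce for that endpoint.

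**Precision of the oocyte comparison.** I use n = 377 per arm (N = 754), because section 8.4 makes the per-protocol set primary and 377 is the planned evaluable number. There are about 5 centres (section 5.1). The unit is the within-arm, within-centre SD of oocyte number. R² is the share of that variance explained by AFC and age together. It is not in the documents, so a range is assumed.

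- Planned ANOVA, half-width = t(N − 6) × √(2/n) = t(748) × √(2/377) = 0.143 SD
- With AFC and age, half-width = t(N − 8) × √[(2/n)(1 − R²)(1 + 2/(N − 9))]. The last factor, 1 + 2/745, is the cost of estimating two slopes.

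| Assumed R² | Half-width (SD) | Ratio to ANOVA | Narrowing | Equivalent extra subjects |
|---|---|---|---|---|
| 0 | 0.143 | 1.001 | −0.1% | −0.3% |
| 0.05 | 0.140 | 0.976 | 2.4% | 5% |
| 0.10 | 0.136 | 0.950 | 5.0% | 11% |
| 0.20 | 0.128 | 0.896 | 10.4% | 25% |
| 0.25 | 0.124 | 0.867 | 13.3% | 33% |

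For R² = 0.25 the ratio is √(0.75 × 1.00268) = 0.867, and the equivalent sample is 1/0.752 = 1.33 times the planned one. Break-even is at R² of about 2/(N − 7) = 2/747, or 0.3%.

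**Simulation check.** In 1000 simulated trials of 754 women in 5 centres, with AFC limited to 8–20 and age to at most 38, the ratio of the SDs of the two estimates was 0.979, 0.913 and 0.842 for R² of 0.05, 0.15 and 0.30. The values of √(1 − R²) are 0.975, 0.922 and 0.837, in good agreement.

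**In oocytes, for illustration only.** At R² = 0.10 the half-width goes from 0.57 to 0.54 if the SD is 4, from 0.71 to 0.68 if it is 5, and from 0.86 to 0.81 if it is 6. These SDs are assumptions.

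**The case against.** The strongest reply is that this is a preference and not an error. ANOVA with treatment and centre is unbiased under 1:1 randomisation and its confidence interval is valid. Oocyte number is one of 14 secondary endpoints, with no margin, no power target and no part in the non-inferiority claim. Section 8.5.3 describes the secondary analyses as further characterisation of the treatment effect. All of this stands, and it is why the point is low priority. It does not remove the point, because the values are collected anyway and using them costs almost nothing.

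The reply is also right that the gain may be small. Besides the limits on AFC and age, FSH dose is set by the investigator in both arms (section 6.2). If dose is chosen partly by AFC or age, the link between those variables and yield weakens. The AFC may also date from up to three months before screening (section 7.2.1).

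A reader might infer more than the documents support in three ways:

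- **A large gain.** A correlation of 0.5 (R² = 0.25) would raise a comparison with 80% power to about 90%. No section supports that correlation, and the plan sets no powered oocyte comparison to which such a figure could apply.
- **A separate harm from chance imbalance in AFC.** Over repeated randomisation this is the same residual variance already counted above, and the ANOVA interval allows for it. It is not bias.
- **A central role for this endpoint.** The documents do not call the between-arm oocyte difference a main mechanistic result. Nor do they call AFC a measure of the follicles available for stimulation: section 7.2.1 gives a size definition and section 5.3.1 an entry range. In section 8.5.2, age and AFC are factors to be evaluated for pregnancy and CLBR, not established predictors of oocyte yield.

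**Conclusion.** The point holds as a free improvement of low priority. The planned analysis is sound, and the oocyte difference it yields is likely to be less precise than the collected data allow. The plausible gain is a confidence interval about 2% to 13% narrower for R² between 0.05 and 0.25, with the lower part of that range more likely. The downside, if AFC and age explain nothing, is about 0.1%.

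The conclusion rests on 377 evaluable women per arm, about 5 centres, and AFC and age together explaining more than about 0.3% of the within-centre variance in oocyte number. The documents do not give that share.

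A reader might infer that the omission weakens the trial's main result. It does not: the CLBR analysis uses a different outcome and method, and both the non-inferiority conclusion and the sample size of 888 are untouched.

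**What to change.** In section 8.5.2 and the synopsis, replace the ANOVA with a pre-specified ANCOVA that has treatment and centre as factors and baseline AFC and age as continuous covariates. Report the adjusted treatment difference with its two-sided 95% confidence interval. Leave out AMH, which is drawn after randomisation, and all stimulation variables. Keep the treatment-and-centre ANOVA as a sensitivity analysis.

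The cost is one sentence in each place and two model terms, or two residual degrees of freedom out of 748. No new data, visits or participants are needed. The change should be made before outcome data are examined, because the trial is open-label and covariates chosen later would carry less weight.

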Both GnRH agonist and GnRH antagonist protocols are widely used in controlled ovarian stimulation (COS); however, there is a persistent debate concerning the reproductive outcomes when comparing the two analogue treatments (Toftager M, 2016). In the most recent Cochrane review, the GnRH antagonist protocol was associated with comparable live birth rate (LBR) and a substantial reduction in the incidence of OHSS when compared to GnRH agonist long protocol in women undergoing ART in none selected population (Hesham G AI,2016).

Comparing with GnRH agonist protocol, the GnRH antagonist protocol is associated with fewer oocytes retrieved, lower OHSS incidence whereas the ongoing pregnancy rate and LBR were similar in supposed normal responders in the recent systematic review and meta-analysis (JS Xiao, 2014). However, the data published in the same year found that among good-prognosis patients, agonist protocol decreased cancellation risk and increased odds of implantation and live birth compared with antagonist protocol using the national surveillance data (D. Grow, 2014).

Overall, there is an ongoing debate regarding the superiority of these two COS protocols in supposed normal responders.

In the other aspect, IVF success has generally been calculated and reported on the basis of LBRs per treatment attempt involving either an intended fresh or frozen-thawed embryo transfer (FET). The continued improvement in reproductive technology has seen an increase in the number of FETs and their associated pregnancy rates. This, combined with an emphasis on reducing multiple pregnancies and increasing single embryo transfers (SETs), means that outcomes per fresh embryo transfer are no longer meaningful to patients and clinicians who want to know their chance of live birth over an entire IVF program. The most appropriate way of reporting this is to estimate the

cumulative chances of success per woman after a number of complete cycles—defined as all fresh and FET attempts resulting from one episode of ovarian stimulation. CLBRs are increasingly proving to be the currency of IVF (DJ. McL 2016).

From fertility counselling perspective, patients undergoing IVF treatments should be informed not only the opportunity of success rate in fresh cycle transfer but also the probability to achieve a live birth after utilization of all cryopreserved embryos.

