5.1 Overall Trial Design and Plan

This is a multicenter prospective study which will observe the cumulative live birth rates (CLBRs) of gonadotrophin-releasing hormone (GnRH) antagonist protocol compared with the standard GnRH agonist long protocol for controlled ovarian stimulation in supposed normal ovarian responders in China. The recruitment period is planned to start on March, 2018 and to last for 2 years, last-subject-out is expected in December 2020.

This study is planned to involve 5 hospitals and recruit 888 female subjects. Relevant data according to study requirements will be recorded in standard case report form (eCRF). When the study initiates, each reproductive center will screen and enroll qualified subjects to enter the treatment. If a subject has entered the study and later discontinues from the treatment cycle, the reason of discontinuing the treatment should be recorded in eCRF.

Each subject will be followed up to 2 years until she has one live birth or all her embryos are used up after one initiated COS, including fresh & frozen-thawed embryo transfers. Subjects who do not obtain live birth but with embryos left for FET in the 2 years follow up will not be analyzed as drop-out cases either and the CLBR for those patients will be calculated and analyzed in appropriate statistical methods.

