6.2 Dosage and Administration

GnRH-a group: GnRH-a types, GnRH-a and FSH doses will be adjusted according to the clinical experiences of investigators in each site. GnRH-a (Diphereline[®] or Decapetyl[®]) 0.1mg administered for about 14 to 20 days for down-regulation is recommended if applicable. Gonal-f[®] will be administered as routinely practiced by investigators. (Daily dose should follow China PI)

GnRH-ant group: The GnRH-ant (Cetrotide[®]) will be initiated in a fixed protocol on stimulation days 5 or 6 per the investigator's ART protocol. Recombinant FSH (Gonal-f[®]) will be administered as routinely practiced by investigators. FSH doses will be adjusted according to the clinical experiences of investigators.

LH supplementation: If there is slow/suboptimal response in follicular development observed by investigators, the rLH (Luveris[®]) will be administered as required. LH supplementation is based on one of the following criteria:

- Having no follicle >10 mm by day 6;
- Low estradiol concentration <200 pg/ml or <732 pmol/L by day 6;
- Poor progression or slowing of follicle growth, i.e., previously 1–2 mm progression/day slowing to less than 2 mm in 3 days.

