6.3 Assignment to Treatment Groups

An Interactive Web Response System will be used in this study for the randomization procedure. Subjects will be randomized and assigned to GnRH-a group or GnRH-ant group. Statistical aspects of randomization, including stratification, will be described in Section 8.2.

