8.3.3 Other Endpoints

To explore the relationship between the number of oocytes retrieved and number of embryos or times of embryo transfer or CLBR

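### The exploratory logistic and Cox models of pregnancy and CLBR name neither arm nor centre, so the oocyte-CLBR relation they estimate can be confounded, mainly by centre

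*Combined protocol and SAP*

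**What the plan says.** Section 8.5.2 gives the regressions one sentence: "univariate/multivariate logistic or cox regression analysis will be performed to evaluate the dependence of Age" (cut at 35 years), and then "AFC, AMH, number of oocytes retrieved, number of usable embryos, times of embryo transfer, and BMI in relation to pregnancy rate or CLBR". That makes seven factors. The sentence mentions no arm term, centre term, fit by arm or stratification. The synopsis carries the same list.

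The paragraph before it in 8.5.2 does name such terms for a different analysis. Oocyte number as an outcome is compared by "analysis of variance (ANOVA) including treatment and center as factors".

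The affected question is set out in 4.3, 7.3.3 and 8.3.3: "To explore the relationship between the number of oocytes retrieved and number of embryos or times of embryo transfer or CLBR". These sections class it under other objectives, as an exploratory endpoint and under other endpoints.

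Nothing elsewhere supplies the missing terms. The general considerations in 8.5.1 cover descriptive statistics and missing data only. Section 6.3 says "Statistical aspects of randomization, including stratification, will be described in Section 8.2", but 8.2 names no stratifying factor, so a convention of adjusting for strata would not bring centre in.

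**The concern.** A factor confounds the oocyte-CLBR relation if it is related to both oocyte number and live birth. The plan's own text gives reason to think that arm and centre could each be such a factor.

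- **Arm.** Section 3 reports that "the GnRH antagonist protocol is associated with fewer oocytes retrieved". It also cites surveillance data in which the agonist protocol had higher odds of live birth.
- **Centre.** In the agonist group, "FSH doses will be adjusted according to the clinical experiences of investigators in each site". Under 7.2.3 to 7.2.5, triggering, retrieval, fertilisation, transfer and luteal support follow each site's routine. These practices can affect both oocyte yield and live birth.

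The plan names arm and centre where oocyte number is the outcome and leaves them out where it is the predictor. At stake is the slope that would be reported for the exploratory objective. The silence also lets the choice of terms be made after the data are seen.

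**Working it through.** **1. The plan's own figure.** The plan gives no figure for these regressions. Its sample size reproduces and is not touched by this point. Per arm, n = (1.960 + 0.842)² × 2 × 0.60 × 0.40 / 0.10² = 7.849 × 48 = 376.7, so 377. With 15% dropout, 377 / 0.85 = 443.5, so 444 per arm and 888 in all.

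**2. Inputs.**
- From the documents: CLBR 60%, 1:1 allocation, 5 centres, 888 women ("This study is planned to involve 5 hospitals and recruit 888 female subjects"), 754 evaluable (2 × 377), and the direction of the arm difference in oocytes.
- Assumed, because the documents give no values: oocyte SD of 5 within arm and centre; true odds ratio of 1.08 per oocyte (log-odds 0.077); the size of the arm gap; the centre spread in oocyte mean and in log-odds of live birth, and the correlation between the two.

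**3. Large-sample check.** Logistic models were fitted to 400,000 simulated women in 5 equal centres, with overall CLBR 60%. The shift is the log odds ratio without arm and centre terms, relative to the one with both.

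| Scenario | OR per oocyte, neither term | OR with arm and centre | Shift in log-OR |
|---|---|---|---|
| No arm or centre effect | 1.079 | 1.079 | 0% |
| Arm: 2 fewer oocytes, acting only through oocytes | 1.080 | 1.079 | 0% |
| Arm: 2 fewer, CLBR equal between arms | 1.078 | 1.081 | -4% |
| Arm: 4 fewer, CLBR equal between arms | 1.067 | 1.079 | -14% |
| Arm: 2 fewer, direct arm OR 0.75 | 1.085 | 1.079 | +7% |
| Centre: SD 1 oocyte and 0.3 log-odds, correlation +1 | 1.090 | 1.080 | +13% |
| Centre: SD 1.5 and 0.4, correlation +1 | 1.101 | 1.080 | +25% |
| Centre: SD 1.5 and 0.4, correlation -1 | 1.054 | 1.079 | -31% |
| Both: arm 2 fewer with CLBR effect offset; centre 1.5 and 0.4, correlation -1 | 1.053 | 1.080 | -33% |
| Both: arm 2 fewer, direct OR 0.75; centre 1.5 and 0.4, correlation +1 | 1.104 | 1.079 | +30% |

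The arm effect is small because a 2-oocyte gap accounts for little of the oocyte variance: (2²/4) / (25 + 2²/4) = 1/26 = 3.8%.

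**4. Check at trial size.** 200 simulated trials of 888 women per scenario, true slope 0.08, with less than perfect centre correlation:
- Centre SDs 1.5 oocytes and 0.3 log-odds, correlation -0.7 or +0.7: mean slope without the terms 0.069 or 0.085; with them 0.081 or 0.079.
- Centre SDs 2 and 0.4, correlation -0.8 or +0.8: without 0.057 or 0.093; with 0.079 or 0.080.

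The last pair amounts to 0.057/0.079 - 1 = -28% and 0.093/0.080 - 1 = +16%, within the range in step 3.

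**5. Scale against sampling error.** SE of the slope ≈ 1/√(N × 0.24 × 25), which is 0.0137 at N = 888 and 0.0149 at N = 754. A shift of -31% is 0.31 × 0.077 = 0.024, about 1.6 to 1.7 SE. A shift of +25% is 0.019, about 1.3 to 1.4 SE. The arm shifts of -4% and +7% are 0.003 and 0.005, at most 0.4 SE.

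**6. Room for the extra terms.** 7 listed covariates + 1 arm + 4 centre = 12 parameters. Non-events among evaluable women: 0.40 × 754 = 302, and 302/12 = 25 per parameter.

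**The case against.** The strongest reply is that the sentence lists factors of interest and is not a model formula. A reader might infer from it that the plan pools arms and centres. The documents do not say so, and they rule out neither arm and centre terms nor fits by arm. That reply stands: what can be shown is that the terms are not named.

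A reader might also infer that the slope is in fact mixed with arm and centre differences. That is not supported either. Arm causes no bias if it acts only through oocyte number, and little otherwise at a 2-oocyte gap. The plan allows centre practice to vary but reports no differences between centres. The upper centre figures use perfect correlation and, at trial size, most of the milder shifts lie within one standard error. No scenario reverses the sign.

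The simulations contain only oocyte number, arm and centre. The planned multivariate model also holds age, AFC, AMH and BMI, which may absorb some centre case-mix. It further holds usable embryos and number of transfers, which arise after retrieval and change what the oocyte coefficient means. Recovery of the assumed slope is therefore not shown for that model.

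Finally, it is tempting to require an arm-by-oocyte interaction test. The stated objective asks for the relation, not whether it differs by protocol, and the power is poor. With 444 per arm, the SE of the slope difference is √2 / √(444 × 0.24 × 25) = 0.027. A difference of 2.80 × 0.027 = 0.077, as large as the whole assumed slope, would be needed for 80% power.

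None of this gives a reason to leave the two terms unstated.

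**Conclusion.** The point holds as a minor gap in the specification of an exploratory analysis. Arm and centre are not named in the pregnancy and CLBR regressions, although both are named for oocyte number in the same section. Followed as listed, the models can give a confounded oocyte-CLBR slope.

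Centre is the main risk, at about -30% to +25%. Arm matters little, at about -4% to +7% for a 2-oocyte gap. Every one of these figures rests on the assumed SD, slope, arm gap and centre spread; the documents can confirm neither the size nor the direction of a centre effect.

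A reader might take the placement under the primary-endpoint heading to mean that the non-inferiority conclusion is at risk. It is not: that test compares the conservative CLBR between randomised arms and uses none of these models.

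**What to change.** In 8.5.2 and the synopsis, add one sentence: the logistic and Cox models of pregnancy rate and CLBR are exploratory and include treatment arm and centre as terms, or are stratified by centre with arm as a term. Reporting the oocyte slope separately by arm is optional and should be described as descriptive only; no interaction test is needed.

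The cost is one sentence in each place and about five parameters. Arm and centre are already recorded for every woman, so no further data, visits or subjects are required.
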